I will provide all study personnel under my supervision copies of the protocol and any amendments, and access to all information provided by Altimmune, Inc., or specified designees. I will discuss the material with them to ensure that they are fully informed about HepTcell and the study.

	_		
Principal Investigator Name (printed)		Signature	
Date (dd-mmm-yyyy)	Site N	umber	

STUDY SUMMARY

Sponsor: Altimmune, Inc.

Study Title: Phase 2, Double-blind, Randomized, Placebo-controlled Study of HepTcell (Adjuvanted FP-02.2) as an Immunotherapeutic Vaccine in Treatment-naïve Patients with Inactive Chronic Hepatitis B (CHB)

Study Number: ALT-301-202

Study Phase: 2

Study Centers: Approximately 35 study centers in North America, Europe, United Kingdom and Asia-Pacific

Number of Patients Planned: Approximately 80 patients with inactive CHB and low hepatitis B surface antigen (HBsAg) levels (10 to 200 IU/mL) randomized 1:1 to HepTcell or placebo and stratified by study center

Duration of Patient Participation: Each patient will participate in the study up to approximately 77 weeks (a 5-week Screening Period, a 24-week Treatment Period, and a 52-week Follow-Up Period commencing after the last dose of study medication at Week 20)

Enrollment Period: Approximately 24 months

Test Product: HepTcell (adjuvanted synthetic fluoropeptide hepatitis B immunotherapeutic vaccine) 150 μg of each fluoropeptide + IC31[®] (500/20 nmol KLK/ODN1a) administered by intramuscular (IM) injection at intervals of 4 weeks for 6 doses

Study Objectives:

Primary Objective: To assess virologic response to HepTcell in treatment-naïve patients with inactive CHB

Secondary Objectives:

- To assess cellular immune response of HepTcell in treatment-naïve patients with inactive CHB
- To assess the safety of HepTcell in treatment-naïve patients with inactive CHB

Study Design: This study is a Phase 2, randomized, double-blind, placebo-controlled, multicenter clinical trial to evaluate the antiviral effects, immunogenicity, and safety of HepTcell in treatment-naïve patients with inactive CHB and low HBsAg levels (10 to 200 IU/mL).

After providing informed consent, patients will undergo a screening period of up to 35 days. A Fibroscan will be performed in all patients who have not had this examination within the previous 12 months before screening, with the exception of

patients with a prior history of liver biopsy within the past 2 years demonstrating no evidence of significant fibrosis.

Patients who meet inclusion and exclusion criteria will be randomized in a 1:1 ratio to receive 6 IM doses of HepTcell or placebo (normal saline) at study visits 4 weeks apart (Days 1, 29, 57, 85, 113, 141). Randomization may occur up to 3 working days before the first day of dosing to allow for the possible preparation of study medication by a central pharmacy and shipment to the study site. Adverse events (AEs) will be monitored, and blood samples will be collected for quantitative HBsAg (qHBsAg), anti-HBsAg antibodies (anti-HBs), hepatitis B virus (HBV) DNA, HBV pre-genomic RNA (pg-RNA), hepatitis B core-related antigen (HBcrAg), and interferon-gamma (IFN-γ) enzyme-linked immunosorbent spot (ELISpot) assay in peripheral blood mononuclear cells (PBMCs). Patients will record any reactogenicity events for 7 days after each administration of study medication in a diary. A visit consisting of a targeted physical examination and safety laboratory tests, including liver panels, will be conducted 7±2 days after administration of Doses 1 and 2 of study medication. These visits may be conducted at home or workplace or, in part, as a telemedicine visit, at the discretion of the Investigator.

If the patient has experienced an acute illness or temperature > 38°C in the 2 days prior to dosing, the administration of study medication and corresponding visit will be delayed until the illness or fever has resolved.

A Safety Committee will conduct regular blinded reviews of all AEs and reactogenicity events. The safety of study participants will also be overseen by an unblinded Data Monitoring Committee (DMC); its responsibilities will be laid out in a DMC charter.

A sentinel cohort of 12 patients (6 receiving HepTcell and 6 placebo) will undergo blinded safety review by the Safety Committee 7 to 10 days after all ongoing patients in the sentinel cohort have completed the respective dose of study medication and will determine the decision to continue at that dose to the expanded cohort. Safety will be assessed in the sentinel cohort before each dose is administered to the expanded cohort. If any of the Stopping Rules (below) are met in one or more patients and the event(s) is deemed possibly or probably related to HepTcell, dosing will be suspended pending DMC review. DMC recommendations may include instituting modifications to ensure the safety of continued dosing or discontinuing the study. If none of the Stopping Rules are met, randomization and dosing may continue in the expanded study cohort. Patients will be unblinded as necessary as to assess the relationship between the study medication and events that meet criteria for Stopping Rules. Safety laboratory testing (Table 3), including liver panel, for Doses 1 and 2 will be obtained during the visits conducted 7±2 days after these doses of study medication. Safety laboratory testing following Doses 3, 4 and 5 will be obtained in the interval

Safety laboratory testing following Doses 3, 4 and 5 will be obtained in the interval from 7 days after dose administration and before the next dose of study medication is administered. Safety labs after Dose 6 will be assessed at the Day 169 visit. Investigators will review the eligibility of all patients prior to dosing to determine if the next treatment is to be administered. Eligibility for the next treatment will include:

1) confirmation that patients did not meet a Stopping Rule (below); 2) confirmation that the pre-treatment liver parameters are within acceptable ranges for treatment (below); 3) confirmation that patients do not have a new confirmed or suspected immune-mediated medical condition (IMC) (Appendix 2). Patients not meeting these criteria will not be treated.

If abnormalities of alanine aminotransferase (ALT), aspartate aminotransferase (AST), total bilirubin, direct bilirubin, or international normalized ratio (INR) are reported after dosing is commenced, the following monitoring and dosing rules will be applied:

Toxicity	Management	Discontinuation of Study Medication
ALT or AST \geq 5× but < 10× ULN, and Total and direct bili < 1.5× ULN, and INR < 1.3 × ULN	Continue dosing Monitor liver panel weekly If ALT/AST fall to <1.5× ULN, stop weekly monitoring	
ALT or AST \geq 10× ULN, and Total and direct bili < 1.5× ULN, and INR < 1.3 × ULN	Interrupt dosing Monitor liver panel weekly If ALT/AST fall to <5× ULN, restart dosing; if ALT/AST fall to <1.5×, stop weekly monitoring	If the event does not resolve in 4 weeks or recurs, consult medical monitor about discontinuing study medication
ALT or AST \geq 5× ULN, and Total or direct bili \geq 1.5× ULN, or INR \geq 1.3 × ULN		Discontinue study medication
ALT or AST $< 5 \times$ ULN, and Total or direct bili $\ge 1.5 \times$ ULN, or INR $\ge 1.3 \times$ ULN	Interrupt dosing Monitor liver panel weekly If total and direct bili fall to <1.5 × ULN and/or INR falls to < 1.3× on 2 consecutive tests, stop weekly monitoring and restart dosing	If the event does not resolve in 4 weeks or recurs, consult medical monitor about discontinuing study medication

For patients with Gilbert Syndrome, the 1.5 × ULN criteria for total and direct bilirubin will be replaced with a 1.5 × ULN for direct bilirubin and there will be no monitoring criteria for total bilirubin [Fontana 2020]. Other etiologies of ALT, AST, total and direct bilirubin, and INR elevations, such liver injury induced by other drugs and other viral infections, should be ruled out and treated accordingly.

If a patient prematurely discontinues study medication on or before Day 169, the Day 169/Early termination procedures will be performed. Patients who prematurely discontinue study medication will remain in the study for follow-on study assessments.

Patients will be followed for 52 weeks after the last dose of study medication (504 days beyond Day 1 for patients who complete the 24-week Treatment Period).

AEs and concomitant medications will be recorded from the signing of informed consent to Day 169, but only medically-attended adverse events (MAEs), new-onset chronic illnesses (NCIs), and IMCs, which will be categorized as AEs, will be followed subsequently. Likewise, concomitant medications will be recorded through Day 169, but only immunosuppressive medications, vaccines, and new HBV treatments or medications associated with MAEs, NCIs, SAEs, hepatitis flares, or hepatic injury will be recorded beyond this point. At the end of the clinical trial, the decision about follow-on treatments and medical care will be made by the patient's medical physician or medical team in accordance with the usual standard of care.

Patients will be required to limit their alcohol consumptions to no more than moderate intake (defined as 2 drinks/day for men and 1 drink/day for women) during their participation in the study.

Risk-factor appropriate surveillance for hepatocellular carcinoma (HCC) may be performed at the discretion of the investigator.

The measures to be taken at each investigative site to minimize the risks of COVID-19 will be communicated to the patient, along with any changes to the risks of study participation that occur as a result of changing local COVID-19 conditions. Study participants will not be prevented from receiving COVID-19 vaccines during their trial participation and will be advised accordingly. If an authorized COVID-19 vaccine has been administered in proximity to a scheduled investigational product (IP) administration, $a \pm 3$ day window is allowed for IP dosing.

Stopping Rules:

In consultation with the DMC, the following Stopping Rules will be applied:

- ALT or AST $\geq 10 \times$ upper limit of normal (ULN)
- INR > 1.3
- Total bilirubin $\geq 1.5 \times$ ULN (excluding patients with Gilbert Syndrome)
- Direct bilirubin $\geq 1.5 \times$ ULN (for patients with Gilbert Syndrome)
- Serious adverse events (SAEs)
- Severe systemic reactogenicity event

Inclusion Criteria:

Patients who meet all of the following criteria may be included in the study.

- 1. Able and willing to provide informed consent
- 2. Men and women 18 to 65 years of age, inclusive
- 3. Body Mass Index (BMI) 18.0 to 34.9 kg/m², inclusive
- 4. Inactive, treatment-naïve CHB with documented HBsAg positivity for at least 12 months before Day 1. (The history of HBsAg positivity may be reduced to 6 months provided HBV anti-core IgM antibodies are negative).
- 5. $qHBsAg \ge 10 IU/mL$ but $\le 200 IU/mL$ in the 12 months prior to screening or from informed consent to randomization

- If a patient has more than one qHBsAg value within 12 months and prior to randomization, the patient will be deemed eligible if any one measurement is within the eligible range.
- 6. AST, ALT, INR, albumin, total bilirubin (excluding patients with Gilbert Syndrome, who will only be eligible for study participation if total bilirubin is ≤ 3.0 mg/dL) and direct bilirubin within normal limits at screening. Note: ALT and AST elevations up to 1.5 x ULN are allowed if evidence of hepatic steatosis, defined as one of the following criteria: 1) fatty liver on ultrasound, or other imaging modality or Fibroscan controlled attenuation parameter (CAP) ≥ 260 dB/m. To qualify under these conditions, HBV DNA must be <2,000 IU/mL, and there must be no history or signs of liver disease other than fatty liver and HBV.
- 7. Negative drug screen at screening unless prescribed by a medical practitioner for medical use (NB, recreational and prescription cannabis is allowed)
- 8. For women of childbearing potential (women who are not permanently sterile [documented hysterectomy, bilateral tubal ligation, salpingectomy, or oophorectomy] or postmenopausal [12 months with no menses without an alternative medical cause]):
 - a. Negative pregnancy test on Day 1
 - b. Willingness to practice a highly effective method of birth control with low user dependency from screening through one menstrual cycle after the last dose of study medication, which include:
 - i. Abstinence
 - ii. Sex only with persons of the same sex
 - iii. Monogamous relationship with vasectomized partner
 - iv. Intrauterine device
 - v. Combined estrogen and progestogen containing hormonal contraception associated with inhibition of ovulation (oral, intravaginal, transdermal)
 - vi. Progestogen-only hormonal contraception associated with inhibition of ovulation (oral, injectable or implantable)
 - vii. Intrauterine hormone-releasing system

Patients who practice true abstinence or who exclusively have same sex partners need not use contraception, provided it is in line with their preferred and usual lifestyle. Periodic abstinence (eg, calendar, ovulation, symptothermal, post-ovulation methods) and withdrawal are not acceptable methods of contraception. Should any such patient stop practicing abstinence, they must use contraception as described above.

- 9. For men with sexual partners of childbearing potential, as defined above:
 - a. Abstinence
 - b. History of vasectomy or surgical sterilization

- c. Monogamous relationship with a postmenopausal or surgically sterilized partner
- d. Willingness to practice a highly effective method of contraception, as defined above, for 90 days after the last dose of study medication and to refrain from sperm donation for this time

The same criteria pertaining to abstinence and withdrawal methods in women of childbearing potential (Inclusion Criterion 8) apply to men with sexual partners of childbearing potential

10. Willingness to comply with all aspects of the study through the entire study period

Patients who fail to meet Inclusion Criteria 5 and/or 6 and otherwise meet the requirements for study participation will be permitted one additional blood draw during the same screening period to requalify. Patients who screen fail for other Inclusion Criteria may undergo rescreening at the discretion of the Investigator and Medical Monitor.

Exclusion Criteria:

Patients who do not meet any of the following exclusion criteria may be included in the study.

- 1. Pregnant or lactating women
- 2. Positive hepatitis B e antigen (HBeAg) at screening
- 3. History of a hepatitis B flare or 1-log increase in HBV DNA or HBsAg in the prior 6 months
- 4. Prior or current history of active or untreated human immunodeficiency virus (HIV), hepatitis C virus (HCV), or hepatitis delta virus (HDV)
- 5. Acute COVID-19, a positive test result for SARS-CoV2 infection, or exposure within 14 days to an individual with acute COVID-19
- 6. Febrile illness (temperature ≥ 38.0 °C) within the past 14 days
- 7. Prior or current history of any underlying liver disease not related to HBV (NB, steatosis, as documented by imaging or Fibroscan CAP, is permitted if ALT and AST are <1.5 x ULN and HBV DNA <2,000 IU/mL and there is no history or signs of liver disease other than fatty liver and HBV)
- 8. Fibroscan > 8.5 kPA at screening, or history of hepatic fibrosis or cirrhosis (NB, a Fibroscan is not required if an examination is performed within 12 months before screening, or a liver biopsy was performed within 2 years before screening and no fibrosis [F1 or greater] was identified.)
- 9. History of cirrhosis or signs of hepatic decompensation, including but not limited to variceal bleeding, ascites, or hepatic encephalopathy
- 10. White blood cell count $< 3,500/\mu L$, neutrophils $< 1,000/\mu L$, hemoglobin < 11 g/dL, or platelets $< 125,000/\mu L$

Note: Individuals of African descent with a white blood cell count $<3,500/\mu L$ will not be excluded for this reason if white blood cell count is $\ge 2,500/\mu L$,

provided that the neutrophil count is $\geq 1,000/\mu L$ and there is no other identified cause of leukopenia.

- 11. Prior treatment with an approved or investigational agent for HBV.
- 12. History of conditions associated with immunocompromise
- 13. History of conditions associated with altered immune response, such as anaphylaxis, angioedema, or autoimmune disease
- 14. Treatments known to affect the immune system, such as corticosteroids (other than topical or inhaled preparations), alkylating drugs, antimetabolites, cytotoxic drugs, radiation, immune-modulating biologics, allergy injections, immunoglobulins, interferons or other immunomodulating therapies, within 30 days of screening
- 15. Uncontrolled diabetes mellitus, defined as Hemoglobin A_1C (Hb A_1C) \geq 10% at screening
- 16. Receipt of live-attenuated replicating vaccines within 30 days or receipt of any other licensed or authorized vaccines (including vaccines intended to prevent COVID-19) within 14 days prior to Day 1
- 17. Change in any chronically administered medication or treatment within 14 days of screening or inability to maintain these medications at the same dose through Day 169 (NB, patients chronically using aspirin, non-steroidal anti-inflammatory agents, antacids, vitamins, probiotics, and over-the-counter medications will maintain their level of intake throughout the study)
- 18. Malignancy within 3 years of screening, excluding non-melanoma skin cancers and carcinoma *in situ* cervical cancer (NB, patients who have undergone prior screening for HCC by imaging or alpha-fetoprotein levels will have negative test results)
- 19. Untreated alcohol or drug abuse
- 20. Planned elective surgery or hospitalization during the study period
- 21. Participation in a prior trial involving HepTcell or FP-02.2
- 22. Known allergy to any of the ingredients in HepTcell
- 23. Receipt of any investigational drug or treatment within 30 days before Day 1 or planned use during the study period
- 24. Any medical, psychiatric, or social condition or occupational or other responsibility that in the judgment of the Investigator would interfere with or serve as a contraindication to protocol adherence, assessment of safety (including reactogenicity), or a patient's ability to give informed consent

Patients who are excluded by Exclusion Criterion 10 but otherwise meet the requirements for study participation will be permitted one additional blood draw to requalify. Patients who screen fail for other Exclusion Criteria may undergo rescreening at the discretion of the Investigator and Medical Monitor.

Efficacy Endpoints:

Primary Efficacy Endpoint:

The proportion of patients achieving virologic response, defined as a 1.0-log reduction in qHBsAg or serologic clearance of HBsAg, Baseline to Day 169

Secondary Efficacy Endpoints:

- Proportion of patients achieving serologic clearance of HBsAg on Day 169
- Proportion of patients achieving serologic clearance of HBV DNA on Day 169
- Changes in qHBsAg, HBV DNA, HBcrAg, and pg-RNA levels, Baseline to Days 85 and 169
- Change in IFN-γ frequency by ELISpot in PBMCs, Baseline to Days 85 and 169

Exploratory Efficacy Endpoints:

- Proportions of patients achieving serologic clearance of HBsAg on Day 505
- Proportions of patients achieving serologic clearance of HBV DNA on Day 505
- Proportion of patients with anti-HBs on Day 505
- Changes in qHBsAg, HBV DNA, HBcrAg, and pg-RNA levels, Baseline to Days 323 and 505
- Change in IFN-γ frequency by ELISpot in PBMCs, Baseline to Days 323 and 505

Safety Endpoints

- Incidence and severity of AEs, MAEs, NCIs, and IMCs
- Incidence and severity of local and systemic reactogenicity events
- Incidence and duration of hepatitis flares, defined as ALT \geq 3 × ULN and \geq 100 U/L
- Changes in ALT, AST, alkaline phosphatase [AP], gamma glutamyl transferase [GGT], bilirubin total and direct, and INR and other laboratory parameters

Safety endpoints will be assessed separately for the 24-week Treatment Period and 52-week Follow-Up Period

Statistical Methods:

Power and Sample Size Assumptions:

A study of interferon- α 2 in a population with inactive CHB reported a mean incremental decrease of 1.3 log-qHBsAg at 24 weeks in those patients completing interferon- α 2 treatment compared to non-treatment. Mean decrease would translate to approximately 50% of patients completing treatment achieving 1.3 log-qHBsAg

response (reduction). To estimate treatment effect in the current study, the proportion of patients achieving a 1.0-log reduction in qHBsAg is estimated as one-half (25% of patients) who achieve this response. Assuming a response rate of 3% on placebo and 25% on HepTcell, 40 patients will be randomized per treatment group to detect a difference in the proportion of patients treated with HepTcell achieving the primary endpoint compared to patient treated with placebo at a 0.05 level of significance (two-sided) with approximately 80% power.

Statistical Analysis:

Population definitions:

Safety Analysis Set: All patients who receive any study medication.

Modified intent to treat (mITT): All randomized patients who receive any amount of study medication, have a baseline and at least one post-baseline efficacy assessment. Patients will be analyzed according to the treatment that they receive. This analysis set will be used for primary and secondary analyses.

Per Protocol (PP): All randomized patients who receive the full designated amount of study medication according to the correct treatment assignment and who have results from HBV serology and viral markers at Day 85.

General:

Baseline is defined as data collected closest to randomization prior to any study medication dosing. All analyses and summary statistics will be presented by treatment group (HepTcell, placebo).

Descriptive statistics, including the numbers and percentages for categorical variables and the numbers, means, standard deviations, medians, minimums and maximums for continuous variables will be provided by treatment.

Patients will be randomized 1:1 to HepTcell or placebo and stratified by study center to minimize imbalances between treatment groups. To assure a 1:1 distribution of HepTcell and placebo (6 patients each of 12 patients) in the sentinel cohort, randomization in this group will not be stratified.

An interim analysis will be performed after all patients complete 24 weeks (6 doses) of treatment or discontinue study medications.

Efficacy Analyses:

Descriptive statistics will be used to evaluate differences in demographic and baseline characteristics.

For the primary analysis, proportions of patients with virologic response, defined as a 1.0-log reduction in HBsAg or serologic clearance of HBsAg, will be compared between HepTcell and placebo groups using Fisher's Exact Test at a 0.05% two-sided level of significance. The same approach will be applied for secondary or exploratory endpoints that are categorical in nature. Patients who discontinue prematurely or have missing data will be considered non-responders for that endpoint. Linear and logistic regression will be employed to examine the effects of baseline factors, such as qHBsAg level, HBV DNA levels, hepatitis B genotype on response.

Changes from baseline in PBMC ELISpot, HBsAg, HBcrAg, pg-RNA and HBV DNA will be analyzed using a mixed model for repeated measures (MMRM) model. The model will include the fixed effects of treatment, stratification factor, week, and treatment-by-visit interaction as well as the continuous, covariate of baseline level. The model will employ an unstructured within patient covariance matrix and a restricted maximum likelihood (ReML) estimation method.

A Kaplan-Meier model will be developed to compare changes between treatment groups in HBsAg clearance and a 1-log reduction in HBsAg over time.

Relationships between hepatitis flares and HBsAg loss and/or decline will be evaluated logistic and linear regression.

No multiplicity adjustments will be made for secondary or exploratory endpoints. Safety and Tolerability:

Quantitative safety data will be summarized using descriptive statistics and frequency distributions. Qualitative safety data will be summarized by frequencies and percentages. All summaries will be presented by treatment arms. AEs will be coded using Medical Dictionary for Regulatory Activities (MedDRA®), Concomitant medications will be coded using World Health Organization (WHO) drug dictionary.

Laboratory evaluations, vital signs assessments and electrocardiogram (ECG) parameters will be summarized by treatment group and protocol specified collection time point. A summary of change-from-baseline at each protocol specified time-point by treatment group will also be presented.

TABLE OF CONTENTS

CLINICA	L PROTOCOL APPROVAL FORM	2
CONFIDI	ENTIALITY AND INVESTIGATOR STATEMENT	3
STUDY S	SUMMARY	4
TABLE C	OF CONTENTS	14
TABLE C	OF TABLES	19
TABLE C	OF FIGURES	19
LIST OF	ABBREVIATIONS	20
1.	INTRODUCTION AND RATIONALE	22
1.1.	Background	22
1.1.1.	Chronic Hepatitis B	22
1.1.2.	HepTCell	23
1.1.3.	IC31	24

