10.2. Sample Size

A study of IFN-α2 in a population with inactive CHB reported a mean incremental decrease of 1.3 log-qHBsAg at 24 weeks in those patients completing IFN-α2 treatment compared to non-treatment. Mean decrease would translate to approximately 50% of patients completing treatment achieving 1.3 log-qHBsAg response (reduction). To estimate treatment effect in the current study, the proportion of patients achieving a 1.0-log reduction in qHBsAg is estimated as one-half (25% of patients) who achieve this response. Assuming a response rate of 3% on placebo and 25% on HepTcell, 40 patients will be randomized per treatment group to detect a difference in the proportion of patients treated with HepTcell achieving the primary endpoint compared to patient treated with placebo at a 0.05 level of significance (two-sided) with approximately 80% power.

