5.3.2.1 Primary endpoint

The primary endpoint will be considered as described in section 4.2.1.

Patients who discontinue early or have missing HBsAg values on Day 169 but who achieve virologic response or serologic clearance of HBsAg on the last available assessment prior to Day 169 will be treated as responders for the primary endpoint; otherwise, patients with early discontinuation or missing HBsAg values on Day 169 will be treated as non-responders.

The proportion of patients achieving virologic response (defined as a 1.0-log reduction in HBsAg or serologic clearance of HBsAg) on Day 169 will be estimated as follows:

(Number of patients having achieved virologic response or serologic clearance of HBsAg to Day 169) / (Number of patients in the corresponding treatment (or overall)) x 100%

This proportion will be compared between treatment groups using Chi-Square Test or Fisher's Exact Test at a 0.05% two-sided level of significance. Fisher's Exact Test will be used if the expected values of at least the 80% of the cells in the contingency table created for estimating proportions are lower than 5.

This proportion will be analyzed using logistic regression models with treatment arm and baseline qHBsAg level as covariate. The analysis of maximum likelihood and odds ratio estimates for patients predicting a 'Yes' in achieving virologic response will be shown.

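### At 40 per arm, Boschloo's exact test would give 83.3% power against 78.0% for the protocol's Fisher test, with the same 5% guarantee; the SAP's chi-square rule does not keep that guarantee

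*Protocol*

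**What the plan says.** The sample-size text (protocol Study Summary and 10.2, repeated in SAP 5.1) reads: "Assuming a response rate of 3% on placebo and 25% on HepTcell, 40 patients will be randomized per treatment group", "at a 0.05 level of significance (two-sided) with approximately 80% power". No allowance for dropout is stated.

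The primary test, in the Study Summary and protocol 10.4.1, is as follows: the proportions "will be compared between HepTcell and placebo groups using Fisher's Exact Test". The level printed there, 0.05%, conflicts with the 0.05 of the sample-size text and with SAP 5.3, which sets proof of concept at a two-sided p below 0.05. I take 0.05 (5%) as intended.

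SAP 5.3.2.1 has the proportions "compared between treatment groups using Chi-Square Test or Fisher's Exact Test". Fisher is used only when 80% or more of the table's cells have expected counts under 5. SAP 5.3.2.2 repeats this for HBsAg clearance and HBV DNA clearance. Protocol 10.6 lets the SAP override the protocol's analyses but says that the primary analysis does not change.

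**The concern.** The design expects few responders, about 1 on placebo (40 x 0.03 = 1.2) and 10 on HepTcell (40 x 0.25 = 10). Fisher's test conditions on the total number of responders, and with counts this small the attainable p-values are widely spaced. The test then uses much less than the 5% it is allowed, and the unused part is lost power. The one proof-of-concept decision rests on this comparison. Under Fisher, 5/40 versus 0/40 gives p = 0.055 and 7/40 versus 1/40 gives p = 0.057. Boschloo's test gives p = 0.033 for both.

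**Working it through.** **Inputs.** 40 per arm, 3% versus 25%, two-sided 0.05, about 80% power (protocol 10.2); Fisher's exact test (protocol 10.4.1); chi-square or Fisher by expected counts (SAP 5.3.2.1).

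**1. The plan's own figure.** The documents do not give the formula used. The usual normal approximation, with mean rate (0.03 + 0.25)/2 = 0.14 and difference 0.22, is

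n = [1.96 x sqrt(2 x 0.14 x 0.86) + 0.8416 x sqrt(0.03 x 0.97 + 0.25 x 0.75)]² / 0.22² = (0.962 + 0.392)² / 0.0484, or 38 per arm.

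At 40 per arm the same formula gives 82.2% power. Fisher by exact enumeration gives 78.0%. Both fit "with approximately 80% power".

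**2. Method.** List every pair (x, y) of responder counts, 41 x 41 tables at 40/40. For a rejection region R:

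- power = sum over R of Bin(x; 40, 0.25) x Bin(y; 40, 0.03)
- size = maximum over a common rate p of the sum over R of Bin(x; 40, p) x Bin(y; 40, p)

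Fisher's R is all tables with two-sided Fisher p of 0.05 or less. Boschloo's R orders tables by that same p-value and takes the largest cut-off that keeps size at or below 5%. Fisher's own region has size below 5%, so Boschloo's cut-off cannot be under 0.05. At 40/40 it is 0.0707. Every Fisher rejection is therefore a Boschloo rejection.

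**3. Results at 40/40.**

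| Test | Power | Maximum size |
|---|---|---|
| Fisher | 78.0% | 3.3% |
| Boschloo | 83.3% | 4.8% |
| Uncorrected chi-square | 88.5% | 5.9% |

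Fisher's maximum of 3.3% occurs at a common rate of 50%. At a common rate of 3% its size is 0.07%, and Boschloo's there is also low, at 0.4%. The fewest HepTcell responders needed for significance against 0, 1 or 2 placebo responders are 6, 8, 9 for Fisher and 5, 7, 9 for Boschloo. Fisher needs 44 per arm to reach 83.3%.

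**4. Other arm sizes (HepTcell/placebo, same rates).**

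| Arms | Fisher | Boschloo | Gain (points) |
|---|---|---|---|
| 40/40 | 78.0% | 83.3% | 5.3 |
| 39/41 | 84.2% | 88.1% | 3.9 |
| 41/39 | 80.5% | 84.1% | 3.6 |
| 38/38 | 74.6% | 80.7% | 6.1 |
| 36/36 | 70.6% | 80.9% | 10.3 |

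**5. The SAP rule.** Within each arm the expected responders and non-responders add up to the arm size, about 40, so at most one of the two can be below 5. Across the table that is at most 2 of 4 cells, or 50%. The 80% threshold is never reached and chi-square is always used. Uncorrected, its true size reaches 5.9% at 40/40. Reversing the rule to the more usual form (Fisher when more than 20% of cells have expected counts below 5) still leaves a maximum size of 5.7%.

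**The case against.** Fisher's test is standard and valid, and 78.0% is a fair reading of about 80%. A reader might infer that the protocol's power statement is wrong. It is not, and choosing a valid but less powerful test is not an error. That stands.

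A reader might also infer that 5/40 versus 0/40 would certainly have been a failed trial. That follows only if the protocol's test governs. Under the SAP rule, uncorrected chi-square gives p = 0.021 for that table and p = 0.025 for 7/40 versus 1/40. Under the SAP the weakness is error control, not lost power.

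The figures 3.3% and 78.0% belong to exactly 40/40. Enrolment is approximate, randomization is stratified over about 35 centres, and the mITT set drops some patients, so equal arms are not assured. One patient moved between arms puts Fisher above 80% (84.2% at 39/41). This stands against treating 78.0% as fixed, but Boschloo gains in every split checked.

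Barnard's score-based exact test reaches 86.2% at 40/40 and looks better still. It is not better in general: at 39/41 it has 86.8% against Boschloo's 88.1%, and it can reject fewer tables than Boschloo. The two also disagree at 4/40 versus 0/40 (p = 0.043 and 0.082), so offering either would leave the primary test undefined.

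Finally, SAP 2 reports that the Week 24 analysis missed the endpoints and that the study is being terminated. A reader might infer that the choice of test cost the trial its result. The documents give no responder counts, so nothing supports that, and changing the primary test now would be post hoc.

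**Conclusion.** The point holds as a cheap improvement to the design. At 40 per arm, Boschloo's test gives 83.3% power where Fisher gives 78.0%, with the same promised 5% limit, and it loses no result that Fisher would have won. Over the nearby arm sizes checked the gain is about 4 to 10 points. With 38 or 36 analysed per arm, Boschloo stays just above 80% while Fisher falls to 74.6% or 70.6%. The SAP's alternative is not a valid way to recover the power, because it always leads to chi-square, which exceeds 5% if uncorrected, and it departs from protocol 10.6.

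This rests on reading the level as 5%, on the plan's rates of 3% and 25%, on chi-square without continuity correction (the SAP does not say), and on arm sizes of 36 or 38 taken only as illustrations. The documents give no dropout figure.

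**What to change.** In the protocol Study Summary, protocol 10.4.1 and SAP 5.3.2.1, name one primary test before unblinding: Boschloo's unconditional exact test, two-sided, at 0.05 (5%). State that the two-sided Fisher p-value is the ordering statistic, because the guarantee of keeping every Fisher rejection depends on that choice. Report Fisher's p-value as supportive. Delete the chi-square/Fisher switching rule, correct the printed 0.05%, use the same test for the HBsAg and HBV DNA clearance proportions, and restate power as about 83% at 40 per arm.

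As a design change this costs a few sentences, with no added patients, visits or data. The test is less familiar than Fisher. I checked its p-values in scipy; the SAP specifies SAS, so the implementation there would need confirming. For this trial the Week 24 analysis has already been unblinded, so Boschloo's test should not be brought in as a new primary test. The change is for the plan as designed and for a future protocol of this kind.
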